Statistical Analysis Plan

Protocol identification number: S62825 / D454/13

Brief title: The effect of split-belt treadmill training on gait in Parkinson's disease.

Study type: Interventional

Principle investigator: [name] / [name]

Brief summary:

People with Parkinson's disease (PD) often show gait impairments such as shuffling gait, short steps and gait asymmetry and irregularity. These gait problems are already apparent in the early disease stages, having an immense effect on daily life functioning. Especially Freezing of Gait (FOG), where the patients are not able to initiate or continue their movement despite their intention to do so. It is thought that lack of gait adaptability could be an underlying cause of FOG. With a split-belt treadmill the speed of both legs can be controlled independently, which forces participants to actively adapt their gait to the new situation. In a previous study performed at our lab results showed that only one session of split-belt training (SBT) where the speed of one leg was reduced, improved gait adaptability and other gait features compared to tied-belt training (TBT). Furthermore, overground turning speed improved after only one single training session and this was even retained 24 hours later, indicating training induced long-term potentiation. Since the short-term effects of SBT are promising the objective of this study is to investigate if 4 weeks of SBT, 3 times a week, has an effect on gait deficits found in individuals with PD, compared to 4-weeks, 3 times a week, of TBT.

Primary outcome:

Participants will be instructed to turn 360 degrees in alternating directions (clockwise/counterclockwise) for 60 seconds. The instruction is to turn as quickly as possible, while still feeling safe doing this. The average overground turning speed will be determined by the use of APDM Opal accelerometers, which will be worn on both shins, wrists and the lower back.

The primary outcome will be the immediate training effect measured at Retest 1 after the 4 week intervention compared to the results of the measurement before the intervention.

Secondary outcomes:

- Change in Retention ST turning speed
- Change in Pre-Post DT turning speed
- Change in Retention DT turning speed

Main analysis:

The main analysis will be based on intention to treat in that participants will be analysed according to the group to which they were allocated irrespective of the extent of intervention received. The primary outcome will be compared between experimental and control group using a constrained longitudinal data analysis approach using mixed model specification. We will consider Hoehn and Yahr stage, freezing status and centre as possible covariates, depending on between group differences and determined in a blind review of the data.

Freezing and other binary secondary outcomes will be examined using logistic regression models or a negative binomial model, with Hoehn and Yahr stage, freezing status, and centre as possible

covariates, see above. Other secondary outcomes will be examined in mixed models for repeated measurements T1, T2 and T3 controlling for centre, Hoehn and Yahr score, including participants with incomplete follow-up information in the analysis.

Sensitivity analysis:

Sensitivity analyses will be conducted to examine the impact of missing data to using worst-case scenario analysis and by exploring a multiple imputation method, if missing data for the primary outcome exceeds 5%. We will also conduct a per protocol analysis in that we will include patients only who had more than 80% compliance or more than 80% of the intensity of training dose. Data on compliance and any adverse events listed in both groups will be collected by the trainers and therefore will not be collected in a blind fashion. No formal interim analyses are planned, but descriptive data of patients included will be compared in the two groups 6 months into the trial for recruitment purposes. The statistical analysis plan will be finalized before the blinding is broken shortly before the main analysis commences.

Secondary analysis

A planned secondary analysis of the primary outcome will be performed within the subgroups of freezers and non-freezers. The planned analysis of the primary outcome will be also performed within the subgroups of participants with UPDRS scores of 26 and under (less severe) and 27 and over (more severe) (1). The comparison of the intervention effect between subgroups will be tested as an interaction.

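### Does offering a negative binomial model for outcomes called binary put the freezing analysis at risk?

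*SAP*

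**What the plan says.** The Main analysis section of the SAP sorts the secondary outcomes into two groups. For the first, "Freezing and other binary secondary outcomes will be examined using logistic regression models or a negative binomial model". The candidate covariates for this group are centre, freezer status and disease stage on the Hoehn and Yahr scale. For the second, "Other secondary outcomes will be examined in mixed models for repeated measurements T1, T2 and T3 controlling for centre"; these models also adjust for the Hoehn and Yahr score. Counts have no group of their own, and the SAP does not say whether freezing is recorded as yes/no, as a count, or both.

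The Secondary outcomes section lists three items: "Change in Retention ST turning speed", "Change in Pre-Post DT turning speed" and "Change in Retention DT turning speed". All three are continuous.

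Two further statements bear on when choices are made. The covariates are chosen "depending on between group differences and determined in a blind review of the data", and that review is described for covariates only. The Sensitivity analysis section adds that "The statistical analysis plan will be finalized before the blinding is broken".

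**The concern.** Logistic regression takes a 0/1 outcome and returns an odds ratio. Negative binomial regression takes a non-negative count and returns a rate ratio. Joining them with an *or* under the label binary leaves the effect measure and the test for freezing open on paper. Because every other secondary outcome goes to mixed models, the only place the text assigns to the count model is, read literally, 0/1 data.

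That would be a poor pairing. On 0/1 data the negative binomial fit reduces to a Poisson fit, whose model-based variance is too large for a binary variable. The test becomes conservative, and a real effect on a common event could be missed. Freezing is also central to the rationale in the Brief summary, so a reader would want its analysis to be sound.

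**Working it through.** The SAP has no figure on this point to reproduce: it states no event rate, arm size, significance level or power for freezing. The check asks how bad the literal reading would be, and then which reading the text supports.

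**Step 1. What the negative binomial fit does on 0/1 data.** Take an arm with n participants, a events, mean m = a/n and size parameter k. The log-likelihood is

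a·log(m) − n(k + m)·log(1 + m/k).

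Since log(1 + x) ≥ x/(1 + x), putting x = m/k gives (k + m)·log(1 + m/k) ≥ m, with equality only as k tends to infinity. The likelihood is therefore highest at zero dispersion, and the fit is Poisson.

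**Step 2. The variance error.** With true risk p in both arms, the approximate standard errors of the log rate ratio are:

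- model-based (Poisson): √(2/(np))
- true: √(2(1 − p)/(np))
- ratio: 1/√(1 − p)

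For n = 50 and p = 0.5, these are √(2/25) = 0.283 and √(1/25) = 0.200, a ratio of 1.41. For p = 0.3 the ratio is 1.20, and for p = 0.1 it is 1.05. The error is material only for common events.

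**Step 3. Power.** Rates and arm sizes are assumed. The figures come from exact enumeration of all two-arm event counts, with two-sided 5% Wald tests and no covariates.

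| Assumed risks | Per arm | Neg. binomial, model-based | Neg. binomial, robust | Logistic |
|---|---|---|---|---|
| 70% vs 50% | 50 | 0.14 | 0.53 | 0.54 |
| 50% vs 30% | 50 | 0.30 | 0.52 | 0.54 |
| 30% vs 10% | 50 | 0.61 | 0.69 | 0.70 |
| 20% vs 5% | 50 | 0.43 | 0.49 | 0.52 |
| 50% vs 30% | 25 | 0.12 | 0.24 | 0.31 |

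A hand check of the first row: log(0.7/0.5) = 0.336. The model-based standard error is √(1/35 + 1/25) = 0.262 and the true one is √(0.3/35 + 0.5/25) = 0.169. Power is about P(Z > (1.96 × 0.262 − 0.336)/0.169) = P(Z > 1.05) ≈ 0.15, close to the exact 0.14.

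Type I error at 50 per arm and p = 0.5 is 0.5% (model-based), 4.0% (robust) and 5.7% (logistic). The model-based version errs towards missing effects, not towards false claims.

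**Step 4. The same model on true counts.** In 4000 simulated trials per setting (control mean 2 or 4, size 0.5 or 1), the negative binomial Wald test had type I error of 4.6% to 5.6% at 50 per arm and 6.3% to 7.2% at 25 per arm. The conservative loss does not arise when the model is used on counts.

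**Step 5. Which reading the text supports.** The sentence covers several outcomes (freezing and others) and names two models, logistic regression first. If every outcome in the group were yes/no, the second model would have no purpose. It makes sense if at least one of them is a count. On that reading the adjective is too narrow and the models are right.

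**The case for a change.** The strongest case for acting is that matching a model to an outcome type is the job of a SAP. This one attempts it and, on its wording, gets the pairing wrong. Nothing else in the document settles the matter: there is no class for counts, the listed secondary outcomes are all turning speed, and the blind review is described for covariates only. One sentence would clear it up, and the only thing given up is a freedom to switch models that a SAP exists to remove.

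The description of the text is accurate and stands: the sentence is loose, and the document does not choose between an odds ratio and a rate ratio for freezing. The consequence does not stand. For harm to occur, someone must fit a count model to a yes/no variable although logistic regression is named first in the same sentence, must keep model-based variance, and must do so for a common event. An estimated dispersion of zero would itself warn that the model is unsuited. Whether freezing is yes/no or a count is an outcome definition that a SAP commonly leaves to the protocol, which is not at hand. A replacement sentence reserving the negative binomial model for counts of freezing episodes would also bring in an outcome that the SAP never mentions.

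**Conclusion.** No change is called for. This is a clerical looseness, most likely the single word binary, and an analyst would resolve it by giving yes/no outcomes to logistic regression and counts to the negative binomial model. On that reading no estimate, test or conclusion moves.

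The loss on the literal reading can be large (0.14 against 0.54 in the worst row), but it rests on assumed rates and arm sizes and on an analysis that few would run. It falls to 0.61 against 0.70 for 30% versus 10%, and to about 0.01 to 0.03 at 50 per arm with robust variance. The primary outcome and the three listed secondary outcomes are outside it. Because the SAP is to be completed before unblinding, the remaining choice should not be steered by unblinded results. That commitment does not promise that this particular *or* will be resolved, but it limits what could go wrong. The conclusion assumes that the analyst matches the model to how each outcome is recorded.

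### Freezing is modelled as a secondary outcome but is not on the SAP's outcome list, and pooling freezers with non-freezers without a fixed freezing-status term could weaken its logistic analysis

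*SAP*

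**What the plan says.** The Brief summary gives freezing of gait (FOG) a prominent place in the rationale: "Especially Freezing of Gait (FOG), where the patients are not able to initiate or continue their movement despite their intention to do so". It then links FOG to what split-belt training targets: "It is thought that lack of gait adaptability could be an underlying cause of FOG". The objective is broader, namely whether training "has an effect on gait deficits found in individuals with PD".

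The primary outcome is average turning speed in a 60-second turning task. The Secondary outcomes section lists three items, all turning speed: "Change in Retention ST turning speed", "Change in Pre-Post DT turning speed", and the dual-task retention change.

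The Main analysis then says: "Freezing and other binary secondary outcomes will be examined using logistic regression models or a negative binomial model". Hoehn and Yahr stage, freezing status and centre are possible covariates in that model. A cross-reference points to the rule for the primary outcome, under which covariates are considered according to differences between the groups, in a blind review of the data. The freezing sentence names no measure, time point or analysis population.

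The Secondary analysis section does separate the two kinds of participant, but for turning speed only: "A planned secondary analysis of the primary outcome will be performed within the subgroups of freezers and non-freezers".

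**The concern.** Two things do not fit together. First, the analysis section treats freezing as a binary secondary outcome, while the outcome list in the same document has no freezing outcome and no binary outcome. A reader cannot tell which freezing measure was pre-specified.

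Second, a freezing-status covariate has a purpose only if freezers and non-freezers are in the same model, so pooling is the natural reading. If people classed as non-freezers seldom freeze in testing, they contribute few events and have little room to improve. A logistic model without freezing status then estimates a mixture that depends on the share of freezers recruited. Randomisation tends to balance freezing status, and a rule that adds covariates when groups differ then tends to leave it out. The planned subgroup analysis does not help, because it does not cover freezing.

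At stake is a secondary result that readers will look for, given the rationale. A real effect among freezers could be reported as weaker than it is, or missed.

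**Working it through.** The SAP gives no sample size, share of freezers or freezing rate, so there is no figure of its own to reproduce. All inputs below are assumptions.

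**Inputs.** N = 50 per arm; share of freezers f = 0.5; post-training freezing in freezers 0.60 (tied-belt) and 0.30 (split-belt); freezing in non-freezers q = 0 in both arms; two-sided 5% test.

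**Freezers only** (25 per arm)
- Odds ratio = (0.30/0.70)/(0.60/0.40) = 0.29.
- z = 0.30/√[(0.60×0.40 + 0.30×0.70)/25] = 0.30/0.134 = 2.24.
- Power ≈ Φ(2.24 − 1.96) = 61%.

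**All participants, no status term** (50 per arm)
- Risk per arm = f×p + (1−f)×q, giving 0.30 and 0.15.
- Odds ratio = (0.15/0.85)/(0.30/0.70) = 0.41.
- z = 0.15/√[(0.30×0.70 + 0.15×0.85)/50] = 0.15/0.082 = 1.83.
- Power ≈ Φ(1.83 − 1.96) = 45%.
- Information kept = (1.83/2.24)² = 0.67, despite twice the sample.

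**Some freezing in non-freezers.** With q = 0.05 the risks are 0.325 and 0.175, the pooled odds ratio is 0.44 and power is 42%.

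**Range.** Over freezer shares of 0.3, 0.5 and 0.7, rates of 30% v 50%, 30% v 60% and 40% v 70%, and q of 0 or 0.05, the pooled analysis keeps 43% to 82% of the freezers-only information. The low end is 40% v 70%, f = 0.3, q = 0.05. The high end is 30% v 50%, f = 0.7, q = 0.

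**Milder effect.** With 40% v 60% in freezers and q = 0, the freezers-only odds ratio is 0.44. Pooled and unadjusted, it becomes 0.62, 0.58 and 0.54 at shares of 0.3, 0.5 and 0.7. Power is 13%, 21% and 31% pooled, against 19%, 29% and 39% in the freezers alone.

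**The other options the SAP leaves open** (first example, f = 0.5)

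| Analysis of all participants | q = 0 | q = 0.05 |
|---|---|---|
| Logistic, no status term: odds ratio | 0.41 | 0.44 |
| Logistic, status in model: odds ratio | 0.29 | 0.35 |
| Log-link ratio, no status term | 0.15/0.30 = 0.50 | 0.175/0.325 = 0.54 |

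The freezers-only values are an odds ratio of 0.29 and a ratio of 0.30/0.60 = 0.50. So with q = 0 neither the status-adjusted odds ratio nor the log-link ratio is diluted, and with q = 0.05 each moves somewhat towards 1.

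Logistic Wald tests with q = 0 give z = 1.77 without the status term, and 2.10 both with it and in freezers only. Simulated power agrees: about 41% unadjusted, against about 56% for either alternative. The status-adjusted model has its own difficulty when non-freezers have no events: its status coefficient separates. In the milder example the coefficient was 27.6 with a standard error of about 13,000, although the treatment estimate was unaffected.

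**The case against.** The strongest reply is that the plan is open, not wrong. It allows a logistic or a negative binomial model and allows freezing status as a covariate, and dilution arises in only some of those combinations. This stands: a reader might infer that the freezing effect is diluted in general, and the working shows that it is not. What remains is that the covariate rule makes the unadjusted logistic model a likely outcome, and that no rule chooses between the two models.

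Other stronger readings also fail:
- That the SAP says freezing will be modelled in all participants. It names no population for this outcome. The intention-to-treat sentence concerns analysis by allocated group. Pooling is a strong inference from the covariate and the absence of a restriction.
- That non-freezers cannot benefit. The SAP defines neither freezing nor freezing status, and prevention of new freezing would be a benefit.
- That a freezing result could not count as pre-specified. The Main analysis itself calls freezing a secondary outcome and gives it a model, and a fuller outcome list may stand in a protocol that is not at hand. The finding is only that two parts of this SAP disagree.
- That freezing is scored in the 60-second turning test. The SAP describes only turning speed there: "The average overground turning speed will be determined by the use of APDM Opal accelerometers".
- That the trial's objective is freezing. The stated objective is gait deficits in general.

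It can also be said that a fixed status term achieves in the example what a freezers-only analysis achieves. That is true when non-freezers have no events. With 5% freezing in non-freezers the adjusted odds ratio is still 0.35 against 0.29, and with none the status coefficient cannot be estimated.

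**Conclusion.** The concern holds in a limited form. The mismatch between the outcome list and the Main analysis is on the face of the SAP and needs no assumption. The loss of power is conditional: it requires pooling, the logistic option, no freezing-status term, and little freezing among non-freezers. Under those conditions and the assumed rates the odds ratio moves from 0.29 to 0.41, power falls from 61% to 45%, and 43% to 82% of the information is kept over the scenarios tried. These figures illustrate the size of a possible loss and do not measure it for this trial.

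The primary outcome and its analysis are not affected. This is a cheap improvement that the sponsor should make before the SAP is finalised, not a flaw that undermines the trial.

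**What to change.** 1. Make the main freezing analysis a comparison of the randomised arms among participants classed as freezers at baseline, adjusted for baseline freezing where it is recorded. Because the class is fixed at baseline, the comparison remains a randomised one.
2. Keep the all-participant model as a supporting analysis, with freezing status in it whatever imbalance is observed.
3. State which model applies: logistic if the measure is binary, negative binomial if it is a count.
4. Reconcile the Secondary outcomes list with the Main analysis by listing the sponsor's own freezing measure and its time point. If no freezing outcome is intended, delete the freezing model.

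The cost is SAP wording. Freezing status is already a planned covariate and subgroup factor, so the classification adds no data collection. The downside is a smaller denominator for the main freezing analysis, and new freezing among non-freezers would appear only in the supporting analysis.

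### The models for freezing and other binary secondary outcomes should adjust for the outcome's own pre-intervention value where it is measured; optional freezing status is only a partial substitute

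*SAP*

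**What the plan says.** The SAP's main analysis section assigns three types of model.

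- **Primary outcome (turning speed):** compared "using a constrained longitudinal data analysis approach using mixed model specification". In such a model the pre-intervention measurement is one of the responses.
- **Freezing and the binary outcomes:** "Freezing and other binary secondary outcomes will be examined using logistic regression models or a negative binomial model". The candidate covariates, none of them certain to enter, are Hoehn and Yahr stage, freezing status and centre. A cross-reference sends the reader back to the selection rule given for the primary outcome, under which covariates enter "depending on between group differences and determined in a blind review of the data".
- **Everything else among the secondary outcomes:** "Other secondary outcomes will be examined in mixed models for repeated measurements T1, T2 and T3 controlling for centre, Hoehn and Yahr score".

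The second group has no baseline value of the outcome and no repeated-measures structure. Freezing status is not defined there. The secondary analysis section uses it as a two-way split, "within the subgroups of freezers and non-freezers".

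**The concern.** For a sign that tends to recur in the same person, the same measure taken before training would usually be expected to carry much of the predictable variation at follow-up. The SAP uses that information for its turning-speed outcomes and leaves it unnamed for this one class.

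Two things are at stake. The first is precision: a null freezing result is harder to read if explainable variation was left in the error. The second is conditional. If the arms happen to differ in pre-training freezing, an analysis that ignores this carries part of the difference into the estimated effect.

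Freezing status helps only in part. It is a class of patient, not the freezing observed at the pre-training test. Whether it enters depends on what the data look like. For a binary outcome other than freezing, it is not a baseline value of that outcome at all.

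**Working it through.** The SAP states no sample size, event rate or effect size for these outcomes, so there is no figure of its own to reproduce. Every input below is an assumption.

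**Inputs.** Half of participants freeze before training; 50 or 25 per arm; two-sided 5% test. Persistence is written as the control-arm chance of freezing at follow-up among those who froze before, against those who did not: 70%/30%, 80%/20% or 85%/10%. The treatment effect is a conditional odds ratio (OR), mainly 0.35.

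**What OR 0.35 means at 80%/20%.** The control odds are 0.8/0.2 = 4 and 0.2/0.8 = 0.25. Multiplied by 0.35 they become 1.4 and 0.0875. The treated risks are 1.4/2.4 = 58% and 0.0875/1.0875 = 8%. This is a large effect.

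**Power, simulated (60,000 trials per setting).** The unadjusted test is the two-proportion score test. The adjusted test is the Mantel-Haenszel score test stratified on pre-training freezing.

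| Per arm | Persistence | OR | Unadjusted | Own baseline |
|---|---|---|---|---|
| 50 | 70%/30% | 0.35 | 59% | 64% |
| 50 | 80%/20% | 0.35 | 42% | 54% |
| 50 | 80%/20% | 0.25 | 63% | 78% |
| 50 | 85%/10% | 0.35 | 25% | 42% |
| 25 | 80%/20% | 0.35 | 26% | 30% |
| 25 | 85%/10% | 0.35 | 17% | 23% |

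At 25 per arm with 70%/30% persistence the gain is 0 to 2 points.

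**Against the covariate the SAP does list.** Stratifying on a freezing status that agrees with pre-test freezing in 85% of participants gives 46% power at 50 per arm, 80%/20%, OR 0.35. The sequence is therefore 42%, 46%, 54%. Own baseline adds 54 − 46 = 8 points over the proxy and 54 − 42 = 12 over no adjustment.

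A separate simulation used logistic models with Wald tests (2,000 trials per setting, treatment log odds ratio −1.2, the same 85% agreement):

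| Per arm | Baseline-to-follow-up OR | Unadjusted | Status proxy | Own baseline |
|---|---|---|---|---|
| 50 | 4 | 73% | 74% | 76% |
| 50 | 10 | 62% | 65% | 71% |
| 50 | 30 | 38% | 45% | 55% |
| 25 | 4 | 45% | 44% | 46% |
| 25 | 10 | 35% | 37% | 37% |
| 25 | 30 | 22% | 24% | 21% |

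In the last row the own-baseline Wald test rejected in only about 2% of null trials. It is conservative there, which helps explain why no gain appears and why the score test at the same size does show one.

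**Shift from a chance imbalance, no treatment effect.** The spurious risk difference is the difference in baseline share times the difference in persistence risks. For a 60% against 40% split:

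- 70%/30%: 0.20 × 0.40 = 8 points
- 80%/20%: 0.20 × 0.60 = 12 points
- 85%/10%: 0.20 × 0.75 = 15 points

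Given that split and 50 per arm, the false-positive rates in these three cases are 12%, 19% and 27% unadjusted, about 7%, 9% and 12% with the 85% proxy, and about 5% when stratified on own baseline.

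**How often such a split arises.** Under simple randomisation with half freezing before training, a gap of 20 points or more in either direction occurs in about 6% of trials at 50 per arm, 15% at 30 and 20% at 25.

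**Overall type I error.** Over all randomisations it was 4.6% to 5.8% in the score-test simulation, for both tests, and 4.2% to 6.7% for the unadjusted Wald test.

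**The case against.** The strongest reply is that the SAP already allows for freezing status in these models. A clear imbalance in pre-training freezing is also the situation most likely to bring it in, since selection follows observed group differences. This stands in part. It means that a wholly unadjusted analysis is the wrong sole comparator, and that the proxy removes much of the shift: at 95% agreement the conditional false-positive rate falls to 5% to 6%, and at 75% to between 8% and 17%. It does not close the gap. The proxy is optional, its agreement with the pre-test measure is unknown, and it does nothing for other binary outcomes.

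A second reply is that the gain may be negligible. With few participants or weak persistence that is true, and the SAP's silence on sample size leaves it open. If freezing is analysed only among freezers, status is constant and a yes/no baseline may vary little, although a baseline count could still be informative.

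Third, the secondary outcomes listed at the start of the SAP are all turning speed, so neither the primary nor any listed secondary outcome is affected. This stands and lowers the priority.

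A reader might infer that the planned test has an inflated false-positive rate. The results do not support that. The 12% to 27% figures apply only to trials with a 60% against 40% split and only when no freezing covariate is used.

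**Conclusion.** The gap is real and cheap to close. No logistic or negative binomial model in the SAP names the outcome's own pre-intervention value, and the one related covariate is an optional two-level proxy. The consequence is lost precision, plus an estimate that moves with chance baseline differences in a particular trial. The overall test remains valid.

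In the central assumed case, own-baseline adjustment is worth about 12 power points over no adjustment and about 8 over the proxy. At 25 per arm the change over no adjustment ranges from nothing to about 6 points at OR 0.35 or similar. All sizes depend on assumed sample size, prevalence, persistence and large treatment effects. The direction of the conclusion at 50 per arm does not depend on the exact values tried.

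Two stronger readings should be avoided. One is that freezing is analysed with no baseline information at all; freezing status may enter. The other is that every binary outcome could be adjusted in this way. The SAP does not define freezing as an outcome, name any other binary outcome, define T1 (taken here as the pre-intervention visit), or show that each such outcome is measured then.

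**What to change.** In the main analysis section, state that each binary or count secondary outcome measured before the intervention will have its T1 value in the model as a fixed covariate: yes/no for a binary outcome, log(count + 1) for a count. Place this covariate outside the blind-review selection. A longitudinal generalised mixed model that includes T1 would serve equally well and would match the approach taken for the turning-speed outcomes. List the outcomes that have a T1 value, and say that the others are analysed without one.

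Report a standardised risk difference (binary) or rate ratio (count) beside the conditional estimate.

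The cost is SAP wording and one degree of freedom, with no new data for outcomes already measured at T1. The conditional odds ratio will not be directly comparable with a crude one, which the standardised estimate addresses. The SAP is to be finalised before unblinding, so the change can be made at that point.

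### The blinding of the covariate choice is not protected: arms are compared at 6 months while primary-model covariates are still to be picked on between-group differences

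*SAP*

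**What the plan says.** Under Main analysis, the primary outcome is compared between groups "using a constrained longitudinal data analysis approach using mixed model specification". The covariates are left open: "We will consider Hoehn and Yahr stage, freezing status and centre as possible covariates", to be settled "depending on between group differences and determined in a blind review of the data". No threshold or other rule says how large a difference brings a covariate in. The models for freezing and other binary secondary outcomes refer back to the same open list.

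Under Sensitivity analysis, the SAP says "No formal interim analyses are planned", but in the same sentence that "descriptive data of patients included will be compared in the two groups 6 months into the trial for recruitment purposes". It then adds: "The statistical analysis plan will be finalized before the blinding is broken shortly before the main analysis commences". Compliance and adverse event data "will be collected by the trainers and therefore will not be collected in a blind fashion"; these are the only data that the SAP describes as not blind.

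The SAP does not say which variables the 6-month comparison covers, or whether group labels are masked in it. It also does not say whether a blind review means pooled data or coded groups.

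**The concern.** Choosing covariates according to observed imbalance is a data-dependent rule. The only protection the SAP gives it is that the review is blind. The 6-month comparison shows the same kind of information that drives the choice, namely differences between arms, and it comes before the choice is made. If labels are open, someone who knows that split-belt participants have, say, a worse Hoehn and Yahr distribution also knows that adjusting for it will move the estimate towards split-belt training. Three optional covariates give three such decisions. The table might also let a reader of it recognise which coded group is which in the later review.

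At stake is less the size of the error than the defensibility of the primary result. A critic could say that the adjustment set was chosen with knowledge of its direction, and the SAP as written gives no answer. The stated purpose, recruitment, does not on its face need a table by arm.

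**Working it through.** **Order of events, from the SAP.**
1. At 6 months, included patients are compared by group (Sensitivity analysis).
2. Later, covariates are chosen on between-group differences in a blind review (Main analysis).
3. Shortly before the main analysis the SAP is finalised, and then the blind is broken (Sensitivity analysis).

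Step 1 precedes steps 2 and 3, because recruitment is still running at 6 months. Between-group differences cannot be seen in pooled data, so the review in step 2 must use coded groups, which the SAP does not say. No sentence separates those who see step 1 from those who decide in step 2.

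**Size of the possible bias.** The SAP gives no sample size, alpha, SD or correlation, so there is no stated figure to reproduce. Assumed: 50 per arm, no true effect, outcome SD 1, two-sided 5% test, and three independent standardised covariates. Each covariate explains R² = 5%, 10% or 15% of the variance (coefficient b = √R²) and acts equally at both visits. The pre-post correlation is 0.75. The selective rule is to adjust only where the imbalance disfavours split-belt training. ANCOVA stands in for the constrained longitudinal model.

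*Imbalance.* The SD of a covariate's mean difference is √(2/50) = 0.20. Keeping only the favourable imbalances leaves on average 0.20 × 0.399 = 0.080 per covariate.

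*Without baseline turning speed.* Bias = 3 × b × 0.080:
- R² 5%: 3 × 0.224 × 0.080 = 0.054 SD
- R² 10%: 3 × 0.316 × 0.080 = 0.076 SD
- R² 15%: 3 × 0.387 × 0.080 = 0.093 SD

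*With baseline turning speed, as in the planned model.* An omitted covariate now contributes b × (1 − slope), where the slope on baseline is (0.75 − kR²)/(1 − kR²) and k is the number of other covariates already adjusted for (0, 1 or 2, with probabilities ¼, ½, ¼). The mean of (1 − slope) is 0.264, 0.280 and 0.299 for the three values of R², so the bias is:
- R² 5%: 0.054 × 0.264 = 0.014 SD
- R² 10%: 0.076 × 0.280 = 0.021 SD
- R² 15%: 0.093 × 0.299 = 0.028 SD

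The standard error of the effect before further covariates is 0.20 × √(1 − 0.75²) = 0.132 SD, so the bias is 0.014/0.132 = 0.11 to 0.028/0.132 = 0.21 standard errors. A simulation of this set-up (8,000 replicates per R²) returned the same three biases, with two-sided rejection of 5.1%, 5.3% and 5.1%. Runs at this correlation span about 4.6% to 5.7%.

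*If only half the sample is in at 6 months (assumed).* The interim imbalance correlates √0.5 = 0.71 with the final one, so the bias falls to 0.014 × 0.71 = 0.010 up to 0.028 × 0.71 = 0.020 SD.

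**The case against.** The strongest defence is that the SAP does not treat the 6-month comparison as breaking the blind: it places unblinding after finalisation. Coded labels, or a preparer outside the analysis team, would satisfy every sentence. Who has access to such tables is commonly set out in a protocol, which is not at hand. This stands. A reader might infer that the covariate review cannot be blind, but the text does not support that. It supports only that the blinding is not protected by anything the SAP states.

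A reader might also infer an undeclared interim look at turning speed. The phrase about descriptive data of included patients, given for recruitment and set against the absence of formal interim analyses, more naturally means patient characteristics. Nothing says that outcomes are included, although nothing excludes them.

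A third inference would be a material inflation of type I error. That needs either a model without baseline turning speed, which is not the planned one, or a choice among covariate sets with final outcomes seen by arm. A 6-month descriptive table cannot supply final outcomes, and the SAP is to be final before unblinding. Nor could recruiters use the table to even out the arms unless they could foresee or control allocation, and the SAP gives no sign of that.

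Finally, the open covariate rule is a weakness even without the 6-month comparison. That is true, and it is why the remedy starts there. The comparison adds possible knowledge of direction to a rule that relies on not having it.

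**Conclusion.** The point holds in a limited form. The SAP orders a comparison by arm before a covariate choice that depends on differences between arms, and it states no safeguard linking the two. The consequence is modest: about 0.01 to 0.03 SD in favour of split-belt training, with rejection staying near 5%. This is conditional on 100 participants, a pre-post correlation of 0.75, R² of 5% to 15% per covariate, covariates acting equally at both visits, open labels and deliberately selective choice. With masked labels or no selection, this bias does not arise. If the covariates acted only on the follow-up measurement, baseline would not absorb their effect, and the bias would approach the 0.05 to 0.09 SD computed without baseline. The case for change rests on the low cost of removing the exposure, not on a large expected error.

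**What to change.** 1. Under Main analysis, prespecify Hoehn and Yahr stage, freezing status and centre as fixed covariates in the primary constrained longitudinal model whatever imbalance is observed, and delete the clause that makes them depend on between-group differences. The SAP already fixes centre and Hoehn and Yahr score for its other secondary outcomes, so this also brings the models closer together. The cross-reference for the binary outcomes should be brought into line.
2. Under Sensitivity analysis, replace the 6-month clause with: *At 6 months, recruitment and baseline characteristics will be summarised for all participants pooled, by centre and not by allocated group; no outcome data will be summarised.*

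The first change alone removes the bias worked out above. The second removes any doubt about an early look at outcomes.

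Cost: a few degrees of freedom in the primary model, and the loss of an arm-level table that recruitment does not need. No data collection or sample size changes.
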